5.1 General Design

Unilateral THA and simultaneous bilateral THA patients will be recruited. They will be evaluated through three stabilometric tests, gait analysis, two strength tests, TUG and pain (NRS). The session trials will be done the day before surgery, seven and forty day after surgery. The stabilometric tasks, the two strength tests and the NRS will be performed also after three days. The stabilometric test will be characterized by "open eyes", "closed eyes" and "oscillations" conditions. The first two stabilometric tests ("open eyes" and "closed eyes") will last 45 seconds and will be repeated three times. Patients will be asked to keep the erected station with the parallel feet placed at an intermalleolar distance of 5 cm. Their arms should be relaxed along their sides. The patient has to maintain the balance looking at a point in front of him placed at 2 meters of distance in "open

eyes" condition. During the "oscillation" task, the subject, will be asked to perform three oscillations on the platforms, one after 10 seconds from each other. The gait analysis will consist of 4 trials in which the subject will be asked to walk on the gaitwalk. During the evaluation session all subjects will wear their underwear and the performance will be recorded through two cameras (eVixta, BTS SpA) in order to check the correct performance. Before the stabilometric tests and gait analysis, the two strength tests will be performed. In the first case patients will be asked to lie in supine position, to keep the hip with the knee completely extended up to 45 ° for 10 seconds. In the second case patients will be asked to lie on his side, to keep the hip abduction with extended knee for 10 seconds. Strength tests will be repeated for the two lower limbs both. The TUG before gait analysis, will consist of standing up from a chair, walking for 3 meters, to turning a cone and to sitting again, the operator will assess the time of the test. The TUG will be repeated for three times after a break of 1 minute and only the best performance will be considered. At the end of each single test the subject will be asked to quantify pain perceived through the NRS scale. This instrument consists of a visual 10 cm line, numbered from 0 to 10, where 0 corresponds to "no pain" and 10 to "maximum pain imaginable". All the tests listed will be performed by a single operator.

6 Statistical consideration

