14 REFERENCES10

1 Background and introduction

Total hip arthroplasty (THA) is an effective treatment for many hip joint diseases, able to improve patients' functional level and quality of life and to make the return to the activities of daily living possible [1] [2]. The improvement in surgical techniques had made the bilateral THA surgery possible, through one-stage procedure [3]. It seems not to be linked to increased in mortality rate or postoperative complications respect to the same two-stage procedure. [4] [5] [6].

The goal of the surgery is not only the pain relief, but also the functional recovery, which could take place through adaptive mechanisms of the non-afflicted limb. Simultaneous bilateral THA surgery doesn't allow these adaptive mechanisms and our clinical observation suggests that in this condition, the recovery of the operated limb could be faster. This is not a new hypothesis, in fact the use of the residual motor potential when adaptive strategies are not possible, has been largely demonstrated in the functional recovery of stroke patients [7]. In this case, the application of movement restrictions to the non-affected body segments and the intensive use of the affected side, promotes the motor and functional recovery [8]. Some authors suggest to apply similar approaches in other pathological conditions [9] [10].

2 Rationale of the study

Actually there are no studies investigating the motor and functional recovery of unilateral THA patients compared to simultaneous bilateral THA patients. Our clinical observation induce to speculate that simultaneous THA patients could achieve better functional and motor recovery of affected limbs caused by the impossibility to develop adaptive mechanisms with the contralateral side.

3 Object of the study

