6.2 Analysis

The statistical analysis will be performed at the end of the study through SPSS 20.0. Categorical variables will be described in terms of proportion, while the continuous variables will be described in terms of mean and standard deviation or median and interquartile ranges. Outcomes measures will be checked for normality through Kolmogorov-Smirnov test. T-Student test will be used to confirm the homogeneity of the demographic and continuous variables before surgery for stabilometric task (weight distribution between the two lower limbs, mid-lateral and anterior-posterior displacement of the CoP, pelvis, hip, knee and ankle kinematic, muscular activation normalized by MVC, timing of the muscle activation respect to the movements of the tibiotarsic joint and activation frequency) , during gait analysis (ground reaction force, spatio temporal parameters, pelvis, hip, knee, ankle kinematic and timing of muscles activation), during the segmental strength test (time of the support of the lower limbs in the position decided by the operator), related to the TUG (execution time of the trial) and to the NRS scale (value from 0 to 10). The inter-group and intra-group differences after will be evaluated by ANOVA test for repeated measurements and then an eventual post hoc analysis will be conducted. The statistical significance value will be set at $\alpha=0.05$.

7 Withdrawal of subjects

The patients that for any reason will decide to, they will be immediately excluded from it. The incompleting acquisitions will be excluded from the analysis.

8 Forms and procedures for collecting data and data managing

An Excel file (Attachment B) will be filled in with demographic variables and outcome measures. It will be secured by a password. Only two investigators will collect the data in order to reduce errors.

9 Ethical consideration

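### No step of testing, trial selection or processing is masked to group, so detection bias is possible: mainly in TUG and strength hold times, less in the platform-based primary measures

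*Protocol*

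**What the plan says.** - **Testing.** Protocol 5.1: "All the tests listed will be performed by a single operator". For the TUG, "the operator will assess the time of the test"; no timing device and no start or stop event is given. The scoring rule is fixed: of three attempts, "only the best performance will be considered".
- **Clothing and video.** On clothing, protocol 5.1 says: "During the evaluation session all subjects will wear their underwear". Sessions are also filmed, and the same section gives the purpose: "performance will be recorded through two cameras (eVixta, BTS SpA) in order to check the correct performance". Who reviews the video, by what criteria, and what follows a failed check are not stated.
- **Repeated trials.** The open-eyes and closed-eyes stance tests are each done three times and gait is recorded in four trials (5.1). No rule says how the repeats are combined or when one is invalid.
- **Exclusion.** Protocol section 7: "The incompleting acquisitions will be excluded from the analysis". The term is not defined and no decision-maker is named.
- **Staff.** Protocol section 8: "Only two investigators will collect the data in order to reduce errors". Whether the testing operator is one of these two is not stated.
- **Expectation.** Protocol section 1, on simultaneous bilateral surgery: "our clinical observation suggests that in this condition, the recovery of the operated limb could be faster".
- **Masking.** Neither the protocol nor the SAP mentions it for the operator, the video check, signal processing or analysis.
- **Endpoints.** Weight distribution and centre-of-pressure (CoP) displacement from the force platforms are primary (3.2.1). TUG and the strength tests are secondary (3.2.2). The SAP describes strength as a hold time in a position that the operator decides.

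**The concern.** The two groups can probably be told apart by sight. An operator working three and seven days after surgery on a patient in underwear, placing markers for pelvis and hip kinematics, is unlikely to miss whether one or both hips were operated on. The protocol states which group it expects to recover faster. Where the outcome depends on a human reading, such as when the TUG clock stops or when a leg has left its required position, a small unconscious lean in one group looks the same as a treatment difference. The platform measures are better protected, but somebody still decides which recordings are complete, and any manual marking of muscle onsets or gait events would be open to the same influence.

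The design is observational, so avoidable measurement bias would add to whatever confounding already exists. Having a single operator removes variation between operators. It does nothing about that operator treating the two groups differently.

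**Working it through.** **What the plan's own figure allows.** The only design figure is 30 per group (6.1). It comes without an effect size, SD or power, so it cannot be reproduced. It can be turned round: with a two-sided 5% test, the difference detectable with 80% power is (1.960 + 0.842) × √(2/30) = 0.72 SD. A bias of 0.3 SD would be 0.3/0.72, about 42% of that difference.

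**Assumptions, none of them from the documents.** No true group difference; two-sided test (the SAP gives 0.05 without sidedness); a t-test at one visit with 58 df; bias in one group only; for stance trials, the three repeats averaged.

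**1. Operator-assessed outcome (TUG time, strength hold time).** A systematic error of b SD in one group gives noncentrality b × √(n/2) = b × √15. For b = 0.2 this is 0.775, and for b = 0.3 it is 1.162. The critical value is 2.00. The noncentral t distribution gives:

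| Error in one group (SD) | Rejection rate |
|---|---|
| 0 | 5.0% |
| 0.1 | 6.7% |
| 0.2 | 11.9% |
| 0.3 | 20.8% |

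**2. Selective dropping of a repeat (platform outcome).** The expected order statistics of three standard normal values are −0.846, 0 and +0.846. Dropping the worst leaves a mean of (−0.846 + 0)/2 = −0.42 within-session SD. Take the within-session SD as 0.4 to 0.8 of the between-patient SD. If the worst trial is dropped for every patient in one group, the bias is 0.42 × 0.4 = 0.17 to 0.42 × 0.8 = 0.34 between-patient SD. Simulation (40,000 runs, 30 per group) gives:

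| Patients in one group with worst trial dropped | Rejection rate, SD ratio 0.4 to 0.8 |
|---|---|
| 10% | 4.9 to 5.1% |
| 25% | 5.3 to 5.8% |
| 50% | 6.3 to 8.9% |
| 100% (upper bound) | 9.7 to 21.4% |

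Parameterised instead by an intraclass correlation of 0.7 to 0.9, dropping in 10 to 50% of patients shifts the group mean by about 0.01 to 0.12 SD and gives 5.0 to 8.0%.

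**3. Link to the planned test.** The SAP specifies repeated-measures ANOVA, and 5.1 includes a session the day before surgery. If the bias is b0 before surgery and b1 afterwards, the group-by-time contrast carries b1 − b0. Equal bias at all visits therefore largely cancels. Bias that appears or grows after surgery, when the operated side becomes visible, does not. The rates above correspond to b0 = 0 and a comparison at one visit, so they show scale and do not predict the error rate of the planned ANOVA.

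**The case against.** The strongest case against is that the primary measures come from force platforms, TUG is secondary with a best-of-three rule fixed in advance, and the study is a non-randomised pilot. Several stronger readings are tempting, and the documents do not support them:

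- *That trials are accepted or rejected on the video.* The stated purpose is to check performance. Nothing says that a failed check leads to rejection rather than a repeat. The only stated exclusion is of incomplete acquisitions, and a 45-second recording that stops early can be identified objectively.
- *That the operator knows the group and holds the hypothesis.* The first is a sound inference from the clothing and the visit timing, but it is not stated. The second is not shown: section 1 gives the team's expectation, not the operator's.
- *That muscle onsets and gait events are marked by hand.* The documents do not say whether this is manual or automatic.
- *That the primary comparison is heavily biased.* The 10 to 21% range needs the worst trial dropped for every patient in one group and none in the other, with trials averaged, which the plan does not specify.
- *That the bias could never be removed.* If all raw files are kept, trials can be judged again. The plan does not say that they will be kept.

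These points narrow the concern and lower its weight for the primary endpoint. They do not answer the absence of masking, of validity criteria and of TUG timing events. The pilot label does not remove a difference in measurement between groups.

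**Conclusion.** The concern holds in limited form. Detection bias is possible and no safeguard is planned. It bears chiefly on TUG time and strength hold time, where an assumed error of 0.2 to 0.3 SD in one group would give about 12 to 21% false rejections instead of 5%. For CoP and weight distribution the exposure is smaller: about 5 to 9% if the worst of three averaged trials is dropped in 10 to 50% of one group's patients. All these sizes rest on assumed bias, assumed SD ratios and a comparison at one visit, and bias that is constant across visits would largely cancel. The documents show an unprotected process, not that bias will occur. The change is worth making because it needs only staff and recordings already planned.

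**What to change.** A cheap improvement, in protocol sections 5.1, 7 and 8 and in the SAP:

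1. Define an incomplete or invalid acquisition by instrument-based criteria, for example whether the full 45 seconds were recorded. Keep every raw file and log each exclusion with its reason.
2. Export signal files under a random code without group or visit. Whichever of the two section 8 investigators does not run the tests applies the criteria, and does any manual EMG or gait-event marking, before groups are attached. State in 5.1 whether the operator is one of those two.
3. Time the TUG from the session recordings with fixed start and stop events, after confirming that the cameras cover the TUG. This makes the time auditable, not masked, because the video can still show the group. Fix the end-point rule for strength hold time in the same way.
4. Run the analysis with groups labelled A and B until the file is locked.

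The cost is file coding and a log. Masking will be partial: asymmetry in the signals can reveal a unilateral patient, and the second investigator may have met some patients. The operator cannot realistically be masked during live testing, so encouragement and instructions at the session remain unprotected.

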6.1 Sample size

This protocol refers to a pilot study and therefore there aren't normative data. In literature we found studies evaluating the postural stability in THA patients, which enrolled 20 subjects [13]. For the following protocol, 30 subjects for each group will be considered in order to estimate the change of these parameters between-groups.

6.2 Analysis

The statistical analysis will be performed at the end of the study through SPSS 20.0. Categorical variables will be described in terms of proportion, while the continuous variables will be described in terms of mean and standard deviation or median and interquartile ranges. Outcomes measures will be checked for normality through Kolmogorov-Smirnov test. T-Student test will be used to confirm the homogeneity of the demographic and continuous variables before surgery for stabilometric task (weight distribution between the two lower limbs, mid-lateral and anterior-posterior displacement of the CoP, pelvis, hip, knee and ankle kinematic, muscular activation normalized by MVC, timing of the muscle activation respect to the movements of the tibiotarsic joint and activation frequency) , during gait analysis (ground reaction force, spatio temporal parameters, pelvis, hip, knee, ankle kinematic and timing of muscles activation), during the segmental strength test (time of the support of the lower limbs in the position decided by the operator), related to the TUG (execution time of the trial) and to the NRS scale (value from 0 to 10). The inter-group and intra-group differences after will be evaluated by ANOVA test for repeated measurements and then an eventual post hoc analysis will be conducted. The statistical significance value will be set at $\alpha=0.05$.

7 Withdrawal of subjects

The patients that for any reason will decide to, they will be immediately excluded from it. The incompleting acquisitions will be excluded from the analysis.

8 Forms and procedures for collecting data and data managing

An Excel file (Attachment B) will be filled in with demographic variables and outcome measures. It will be secured by a password. Only two investigators will collect the data in order to reduce errors.

9 Ethical consideration

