3.2 End-points

3.2.1 Primary endpoints

The primary endpoint the evaluation of postural stability and the weight distribution during a stabilometric task performed in "open eyes" and "closed eyes" conditions, and during a "voluntary swing" condition. The postural stability and weight distribution will be evaluated through two force platforms (P-6000 BTS SpA). The platforms will calculate the weight distribution between the two lower limbs and the antero-posterior and mid-lateral displacement of the Centre of Pressure (CoP) applied on the ground. An optoelectronic system with passive markers composed of six infrared cameras (Smart DX, BTS SpA) and 4-channel surface electromyography (FREEEEMG 1000, BTS SpA) will also be used. The markers will be placed on anatomic bony landmark according to the Davis model in order to reconstruct the pelvis, hip, knee and ankle kinematic on the sagittal plane during the stabilometric task [11]. The surface electromyography will be placed on the anterior tibialis and gastrocnemius medialis of both limbs, according to SENIAM recommendation in order to evaluate the muscles activations normalized respect to the maximum voluntary contraction (MVC), the timing of muscle activation respect to the movements of the tibiotarsic joint during the "voluntary swing" and the frequency of activation during the three trials [12].

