4.1 Inclusion criteria

- Age between 40 and 65 years old.
- THA surgery for primary or secondary arthrosis.
- THA surgery for primary osteonecrosis.
- Walking ability for at least 50 m without aids.

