4.2 Exclusion criteria

- THA surgery for severe dysplasia (Crowe III e IV).
- THA surgery for ankylosis, sub-ankylosis or surgical fusion of the hip joint.
- THA surgery for a traumatic event.
- THA surgery after previous femoral and / or pelvic osteotomy
- Partial or total THA revision
- Concomitant presence of neurological or musculoskeletal disorders that could affect motor and functional recovery.

5 Study design

The study is a prospective observational study.

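### Baseline t-tests cannot establish that non-randomised groups are comparable, and the repeated-measures ANOVA that follows does not say which term tests the group hypothesis or how the pre-operative value enters it

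*Protocol*

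**What the plan says.** Protocol section 5 states: "The study is a prospective observational study". Patients having unilateral surgery are compared with patients having simultaneous bilateral surgery.

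On comparability, Protocol 6.2 says "T-Student test will be used to confirm the homogeneity of the demographic and continuous variables before surgery". The list that follows covers the stabilometric, gait, strength, TUG and pain measures. No equivalence margin is given, and nothing is said about what happens if a test is significant.

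On the main analysis, the same section says "The inter-group and intra-group differences after will be evaluated by ANOVA test for repeated measurements", with post hoc analysis if needed and alpha 0.05. The SAP repeats this text and adds no model term, role for the pre-operative value, or covariate.

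Protocol 6.1 gives the purpose of the sample: "30 subjects for each group will be considered in order to estimate the change of these parameters between-groups". Under Protocol 5.1, stabilometry, strength and pain are measured the day before surgery and at days 3, 7 and 40. Gait and TUG are measured the day before surgery and at days 7 and 40.

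**The concern.** The protocol's own rationale makes a pre-operative difference plausible. Section 1 describes "functional recovery, which could take place through adaptive mechanisms of the non-afflicted limb", and argues that bilateral patients do not have this route. The primary endpoint includes a measure on which the groups might therefore differ before any operation: "The platforms will calculate the weight distribution between the two lower limbs".

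Eligibility narrows the contrast between groups, for example through "Age between 40 and 65 years old" and the exclusion "Concomitant presence of neurological or musculoskeletal disorders that could affect motor and functional recovery". It does not make the groups exchangeable.

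Two things are then left open. The baseline t-tests are asked to establish something they cannot establish. The ANOVA can be read in at least two ways: the word *after* in 6.2 can mean post-operative visits only, while *change* in 6.1 points to group-by-time with the pre-operative visit included. If the groups differ before surgery, a post-operative group effect carries that difference into the result. The published between-group conclusion could then describe who was selected for which operation rather than how they recovered, and the choice of reading could be made after the data are seen.

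**Working it through.** **Inputs from the documents.** 30 per group (Protocol 6.1); alpha 0.05 (Protocol 6.2), taken as two-sided because sidedness is not stated; one pre-operative and three post-operative visits for the primary endpoint (Protocol 5.1). The documents give no SD, effect size, power or correlation, so they contain no figure to reproduce.

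**Step 1: what the baseline t-test can show.** This needs only n and alpha.
- Standard error of a difference, in SD units: √(2/30) = 0.258.
- 95% CI half-width: t(0.975; 58) × 0.258 = 2.002 × 0.258 = 0.52 SD.
- Power (noncentral t, 58 df, noncentrality d/0.258): d = 0.3 gives 1.16 and 21%; d = 0.5 gives 1.94 and 48%; d = 1 gives 3.87 and 97%.

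A 0.5 SD imbalance is thus missed in 52% of trials. A 1 SD imbalance would nearly always be seen; the gap there is that no action follows.

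**Step 2: what the ANOVA readings do with a pre-operative difference.** Assumptions, none from the documents: no effect of surgery type; pre-operative difference D = 0.5 SD; a fraction λ of it present at every post-operative visit; SD 1; compound symmetry with correlation ρ from 0.3 to 0.7; complete data.

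Variance of one patient's score, and expected group difference:
- Group effect, three post-operative visits: variance (1 + 2ρ)/3, difference λD.
- Group effect, all four visits: variance (1 + 3ρ)/4, difference D(1 + 3λ)/4.
- Change (post-operative mean minus pre-operative value): variance 4(1 − ρ)/3, size of difference (1 − λ)D.
- Post-operative mean adjusted for the pre-operative value: expected difference D(λ − ρ), because the regression slope is ρ.

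For the first three, the noncentrality is the difference divided by √(variance × 2/30). Example, ρ = 0.5, λ = 1, post-operative visits only: variance 0.667, noncentrality 0.5/√(0.667/15) = 2.37, rejection 64.5%. With all four visits: variance 0.625, noncentrality 2.45, rejection 67.3%. The interaction F test and the adjusted contrast (with three further covariates of no effect) were simulated.

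Rejection rates at D = 0.5 SD; ranges are over ρ = 0.3 to 0.7:

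| Contrast | Fully persists | Half persists | None persists |
|---|---|---|---|
| Group effect, post-operative visits | 57–74% | 19–26% | 5% |
| Group effect, all visits | 58–79% | 27–41% | 8–11% |
| Group-by-time F | about 5% | 12–22% | 37–70% |
| Change from baseline | 5% | 17–33% | 50–85% |
| Baseline-adjusted | 16–47% | 5–10% | 13–61% |

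The adjusted contrast comes close to 5% in the middle column because λ is then close to ρ, and exactly equal at ρ = 0.5. That is a feature of the scenario, not general protection.

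Where the difference does not fully persist, the groups really do change by different amounts. A rejection by change or group-by-time is then false only as a causal statement about surgery type.

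**Step 3: does passing the t-test protect?** Only in part. With D = 0.5 SD and full persistence, among simulated trials whose baseline t-test is non-significant, the post-operative group effect is still falsely significant in 46% at ρ = 0.5 (64% at 0.3, 30% at 0.7).

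**The case against.** The strongest defence is that this is a self-described pilot with a broad aim, that the words inter-group and intra-group already imply group and time factors, and that the sizes in Step 2 rest entirely on assumed imbalance, persistence and correlation. Much of this is fair. Pilot status can excuse the absence of a power calculation, and the percentages are illustrations. It does not excuse leaving the hypothesis test undesignated when alpha is fixed and a manuscript is planned (Protocol section 12). The implied factors do not settle whether the inter-group test is the group effect or group-by-time. Step 1 depends on no assumed correlation.

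Several stronger readings are tempting, and the documents do not support them:
- A reader might infer that the pre-operative visit is unused. It is used, in the baseline t-tests; what is unstated is its role in the ANOVA.
- A reader might infer that 30 per group is the defect. A larger sample would narrow the interval, but a non-significant test would still not demonstrate equality.
- A reader might infer that every passing t-test leaves 0.5 SD open. That holds for the 95% interval. A formal equivalence test uses the 90% interval, with half-width 1.672 × 0.258 = 0.43 SD, and at a 0.5 SD margin succeeds about 22% of the time when the true difference is zero. The plan specifies no such test.
- A reader might infer that baseline adjustment is the correct remedy. Protocol 6.1 points to change, and the adjusted contrast still rejects in 16–47% when the difference fully persists.

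**Conclusion.** The concern stands and should be fixed. The t-tests cannot do what the plan asks of them, and no action is tied to their result. The ANOVA neither designates the term that tests the hypothesis, nor places the pre-operative visit as a level or covariate, nor names any adjustment. Followed literally, the plan permits an unadjusted post-operative group effect that imports a pre-operative difference.

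The firm figures are 21% and 48% power at 0.3 and 0.5 SD, and the 0.52 SD half-width. The 57–79% against about 5% is conditional on no effect of surgery type, a fully persisting 0.5 SD difference, compound symmetry and correlation 0.3 to 0.7. It shows that the readings can disagree. It is not a forecast that this study will reach a false conclusion, since the documents do not establish that a pre-operative difference exists. No contrast examined holds 5% under every pattern of persistence, so one analysis alone is not enough.

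**What to change.** In Protocol 6.2 and the SAP:

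1. Replace the homogeneity t-tests with a description of baseline by group, using standardised differences.
2. Name one primary inter-group contrast that uses the pre-operative value, state the post-operative visit or visits it covers, and report it with a 95% CI. It can be the between-group difference in change from baseline (group-by-time with the pre-operative visit as a level, which matches Protocol 6.1), or the post-operative difference adjusted for the pre-operative value. The choice is the sponsor's and should be justified.
3. Pre-specify the other contrast as a sensitivity analysis, and state in advance that disagreement will be reported as uncertainty.
4. Do not use an unadjusted group main effect as the inter-group test.
5. State that residual confounding by indication remains. Further adjustment is optional and should be justified. Age, sex and BMI can be derived from items that Protocol 9.2 places on the case report form; diagnosis (arthrosis or osteonecrosis) could be added if recorded.

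The cost is SAP wording and slightly more analysis for 60 patients, with no new data needed for items 1 to 4. The downside is two estimates that may disagree.

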9.2 Subject identification – Personal Data protection

All records identifying the subject must be kept confidential and, to the extent permitted by the applicable laws and/or regulations, not be made publicly available. The name of the patient will not be asked for nor recorded at the Data Center. A sequential identification number will be automatically attributed to each patient registered in the study. This number will identify the patient and must be included on all case report forms. In order to avoid identification errors date of birth, sex, weight height will also be reported on the case report forms. Only people who are actively involved in the study can access to the database. Each subject will be informed by means of an appropriate data protection module and each of them will also be sign an informed consent without which he / she will not be involved in the study.

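### CoP displacement and spatio-temporal gait parameters are compared between non-randomised groups with no adjustment for height or sex, so comparisons of level, though largely not of change, are open to body-size imbalance

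*Protocol*

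**What the plan says.** - **Design.** Protocol section 5: "The study is a prospective observational study". Section 5.1: "Unilateral THA and simultaneous bilateral THA patients will be recruited". The operation defines the group, and no matching, stratification or balancing is described.
- **Size.** Section 6.1: "30 subjects for each group will be considered in order to estimate the change of these parameters between-groups". No effect size, SD or power is given.
- **Outcomes.** Section 6.2, repeated in the SAP, names "mid-lateral and anterior-posterior displacement of the CoP" for the stabilometric task and "spatio temporal parameters" for gait. These words stand in the sentence on the pre-surgery check, which is the only list of analysis variables in 6.2. Section 3.2 makes the first primary and the second secondary.
- **Analysis.** A Student t test before surgery is meant to show that the groups are alike on demographic and outcome variables. Repeated-measures ANOVA with possible post hoc tests then follows, at alpha 0.05. No covariate is named, and neither is the ANOVA term that decides the question.
- **Scaling.** EMG amplitude is normalised to maximum voluntary contraction. No other normalisation is mentioned.
- **Body size.** Section 9.2: "date of birth, sex, weight height will also be reported on the case report forms". The reason given there is to prevent identification errors. Under 5.1 every patient stands with "parallel feet placed at an intermalleolar distance of 5 cm".

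**The concern.** Sway and gait measures can plausibly depend on body size: step length tends to rise with height, and the foot spacing is the same for a short and a tall patient. Patients who receive one-stage bilateral surgery need not have the same sex mix or height as those who receive unilateral surgery, and nothing in the design makes them alike. If they differ, a comparison of post-operative levels mixes that difference with any effect of the operation. A primary result on CoP displacement could then be read as better or worse stability when part of it reflects who was operated on. Height and sex are already collected, so the exposure is avoidable.

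**Working it through.** **No figure to reproduce.** The 30 per group has no stated effect size, SD or power behind it. For orientation, with a two-sided alpha of 0.05 (sidedness is not stated), the normal approximation d = (z for alpha + z for power) x sqrt(2/30) gives d = 0.72 at 80% power and 0.84 at 90%.

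**Inputs.** From the documents: 30 per group, alpha 0.05. Assumed, because the documents give no values: height SD 9 cm, male-female height gap 13 cm, height-outcome correlation r of 0.3 to 0.5, and a difference in the share of men of 20 or 30 percentage points.

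**Step 1: does the pre-surgery t test protect?** Power from the noncentral t with 58 df and noncentrality d x sqrt(30/2):

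| Height imbalance | Chance of p < 0.05 |
|---|---|
| 0.3 SD | 21% |
| 0.5 SD | 48% |
| 0.8 SD | 86% |

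A moderate imbalance is missed about half the time or more. A t test also does not suit sex, and the plan attaches no consequence to a significant result.

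**Step 2: from sex mix to height.** 0.20 x 13 = 2.6 cm, and 2.6/9 = 0.29 SD. 0.30 x 13 = 3.9 cm, and 3.9/9 = 0.43 SD. With a gap of 11 to 15 cm and a within-sex SD of 6.5 cm instead, 20 points gives 0.26 to 0.30 SD.

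**Step 3: one between-group comparison of levels, no true difference.** Spurious difference = r x height imbalance in SD. The rejection rate comes from the same noncentral t.

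| Difference in sex mix | r | Spurious difference | False-positive rate |
|---|---|---|---|
| 20 points | 0.3 | 0.087 SD | 6.3% |
| 20 points | 0.5 | 0.144 SD | 8.5% |
| 30 points | 0.3 | 0.130 SD | 7.9% |
| 30 points | 0.5 | 0.217 SD | 13.1% |

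**Step 4: the planned ANOVA.** This was simulated with two groups of 30, four visits, no true group difference and 3,000 runs per cell. The height effect was additive and constant over visits.

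| r | Height imbalance | Group main effect | Group-by-visit |
|---|---|---|---|
| 0.3 | 0.3 SD | 7.4% | 4.9% |
| 0.5 | 0.3 SD | 9.4% | 5.0% |
| 0.3 | 0.5 SD | 10.0% | 5.3% |
| 0.5 | 0.5 SD | 18.7% | 5.6% |
| 0.5 | 0.8 SD | 40.9% | 5.0% |

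The main effect is more exposed than a single visit because averaging over visits removes noise but not the offset. With a multiplicative height effect, group-by-visit stayed at 5.1% to 5.6%, apart from 7.8% in the most extreme case (exponent 2, 0.8 SD). With the height effect removed at a 0.5 SD imbalance, the main effect returned to 4.7% (additive) and 5.7% (multiplicative).

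**Step 5: is dividing by height a safe remedy?** Assume mean height 170 cm, so height CV = 9/170 = 5.3%, with outcome CV 10% and r = 0.3. To first order, the correlation of outcome/height with height is (0.3 x 0.10 - 0.053)/sqrt(0.10^2 + 0.053^2 - 2 x 0.3 x 0.10 x 0.053) = -0.23. The height effect is reversed, not removed. With outcome CV 15% the same formula gives about -0.06, so division works or fails depending on figures the documents do not supply.

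**The case against.** The strongest reply is that the study is about recovery. Section 6.1 speaks of change between groups, and every patient is measured the day before surgery. A constant height or sex offset cancels in within-patient change, and step 4 bears this out. This stands, and it confines the point to comparisons of level. It does not remove the point, because 6.2 plans inter-group differences and post hoc tests without saying which term decides.

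Other readings that a reader might infer are too strong:

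- *That outcomes are analysed in absolute units.* Neither document gives a unit, and step length, stride length and gait speed are not named. Spelling out normalisation for EMG alone makes unscaled analysis a fair guess, but what can be said is that scaling is not stated.
- *That height is never used.* The pre-surgery check covers demographic variables, plausibly including height. What is missing is any use in the between-group model.
- *That the fixed foot spacing is a defect.* It is ordinary standardisation of the test.
- *That the groups do differ in height or sex.* Nothing in the documents shows this, and every magnitude above is assumed.

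It is also fair to say that height is one possible confounder among several. It is singled out because it is already recorded and bears on the primary measure.

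**Conclusion.** The point holds in conditional form, as a minor one. If inference rests on the group main effect or on a comparison at one visit, the plan leaves it open to height or sex imbalance, and the homogeneity test is too weak and has no consequence. Under the stated assumptions, a 20 to 30 point difference in sex mix produces about 0.09 to 0.22 SD of spurious difference and 6% to 13% false positives per comparison. The larger main-effect rates need height imbalances of 0.5 SD or more. If inference rests on group-by-visit, the effect is close to nil. The documents do not support the broader inference that the recovery comparison as a whole is biased by body size.

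**What to change.** In Protocol 6.2 and the SAP:

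1. Add height and sex as covariates to the between-group comparisons of CoP displacement and of the length and speed gait parameters, and list those gait parameters by name. Use covariates throughout and do not divide by height.
2. Name group-by-visit, or change adjusted for the pre-surgery value, as the decisive contrast.
3. State the unit of each outcome and report unadjusted values descriptively.

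The cost is SAP wording and two degrees of freedom. No new data are needed and the 30 per group is unchanged.
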